9.1 Definition of analysis sets

The following analysis sets have been defined for this study:

All Study Participants Set: The All-Study Participants Set (ASP) consists of all study participants that sign the informed consent form. This set includes screening failures.

Randomized Set: The Randomized Set (RS) will consist of all participants randomized into the study.

Safety Set – as Randomized: The Safety Set as randomized (SS-r) consists of all study participants who received any study treatment, including during the run-in period. The study participants will be analyzed according to the randomized treatment groups during the specific treatment period.

The SS-r will be used for production of safety analysis by visit, as well as demographics and immunogenicity analyses.

Safety Set – as Treated: The Safety Set as treated (SS-t) consists of all study participants who received any study treatment including during the run-in period. If a participant received at least one dose of active treatment during a given treatment period, participant will be allocated to active treatment group at the given treatment period and any period thereafter in the SS-t as treated analysis set (most conservative approach). For analysis purposes, the SS-t will be used for tabulating AEs by treatment where AEs are assigned to the active treatment group based on the onset of AE relative to the first dose of active treatment.

The SS-t will be used for safety overall analysis.

Full Analysis Set: The Full Analysis Set (FAS) consists of all study participants in the SS-r who have a Baseline value and at least one post-Baseline efficacy endpoint assessment. Study participants who receive at least one dose of treatment not per randomization schedule will be excluded from the FAS.

This analysis set will be used for the summaries and analyses of primary, secondary, and exploratory efficacy variables data.

Pharmacokinetic Set: The Pharmacokinetics Set (PKS) consists of all study participants in the SS-r who have at least one dose of active IMP and at least one measurable PK concentration including below limit of quantification (BLQ). The PKS will be used for all PK summaries and analyses. If a study participant in the PKS is missing individual time points or are otherwise unobservable, they will be included in the PKS but those time points will be omitted from the PK summaries, as appropriate.

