9.4 Planned safety and other analyses

9.4.1 Safety analyses

All safety variables will be analyzed by descriptive methods and presented by sequence and by period (Period 1, Period 2, or SFU) showing the treatment when the safety event occurred. In addition, events will be summarized by treatment and period. Any events in the SFU Period from sequence 1 and 2 will be tabulated under active treatment.

- Frequency and intensity of TEAEs from Baseline to SFU, and
- TEAEs leading to withdrawal of IMP

will be the safety variables analyzed in this study and will be included in the summary tables.

The overall frequency during the study period will be presented for each of the safety variables, as well as separately by System Organ Class, high level term, and preferred term (Medical Dictionary for Regulatory Activities [MedDRA®]). The data will be displayed as number of

study participants experiencing the event, percentage of study participants, and number of events. Additional tables will summarize the safety variables by maximum intensity, by intensity, and by relationship to study drug.

Laboratory evaluations and vital signs will be analyzed over time. Possibly clinically significant treatment-emergent abnormalities will be listed and summarized by visit for each treatment group.

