## 1 INTRODUCTION

The purpose of this Statistical Analysis Plan (SAP) is to provide all information that is necessary to perform the required statistical analysis of study FM0001. The SAP summarizes what will be provided in the tables, figures and listings (TFLs) to be included in the final clinical study report (CSR) according to the protocol, as well as defining the output to be generated for safety signal detection (SSD) and for the Early Readout Analysis. The TFL specifications are contained in a separate document and are based on the UCB Standard TFL Shells. The requirements for the Early Readout Analysis will be defined in the Unbinding Plan and the Safety Monitoring Committee (SMC) procedures will be defined in a separate charter.

Unless specified in the sections below, the study will be analyzed as described in the most recent version of the protocol. If a future protocol amendment necessitates a substantial change to the statistical analysis of the study data, this SAP will be amended accordingly. In addition, if the methodology for the analysis of primary or secondary endpoints must be modified or updated prior to unblinding, a SAP amendment will be required. If, after unblinding, additional analyses are required to supplement the planned analyses described in this SAP, these changes will be described in the CSR together with the associated rationale. Other minor changes to non-key analyses will also be documented in the CSR.

The content of this SAP is compatible with the International Council for Harmonisation (ICH)/Food and Drug Administration (FDA) E9 Guidance documents (Phillips et al, 2003).

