**Table 1-1: Objectives and Estimands/Endpoints**

Objectives	Endpoints/Estimands
	

Population level summary: mean difference in average BPI-SF interference score between the two treatments

Secondary	

To assess the safety and tolerability of rozanolixizumab in study participants with severe FMS

To evaluate the efficacy of rozanolixizumab for treatment of study participants with severe FMS

	

Occurrence of TEAEs during the study

TEAEs leading to withdrawal of IMP

BPI-SF average interference score after 24 weeks of treatment

FIQR score after 10 weeks of treatment

Mean 7-day average daily pain score (Pain NRS) after 12 weeks of treatment

Mean 7-day fatigue score (Fatigue NRS) after 12 weeks of treatment

Exploratory	

To assess the PK of rozanolixizumab in study participants with severe FMS

To evaluate the efficacy of rozanolixizumab for treatment of study participants with severe FMS

To assess the safety and tolerability of rozanolixizumab in study participants with severe FMS

To evaluate the incidence and emergence of ADA of rozanolixizumab in study participants with severe FMS

To assess the PD effect of rozanolixizumab in study participants with severe FMS

To assess the effect of rozanolixizumab on exploratory biomarkers in study participants with severe FMS

	

Plasma concentration of rozanolixizumab prior to dosing on Week 13 and Week 25

Pressure pain threshold as measured by pressure algometry

Change from Baseline in vital signs and laboratory results at scheduled assessments during the Treatment Period through the Run-Out Period

Antidrug antibody incidence at scheduled assessments during the Treatment Period

Value (absolute) and change from Baseline (absolute and percentage) in serum total IgG and IgG subclasses at scheduled assessments during the Treatment Period

Assessment of IgG binding in in vitro cell assay at scheduled assessments during the Treatment Period and the Run-Out Period

Assess genetic variation for potential effects on disease progression and/or drug

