### **5.6.2 Adverse Events**

All AEs will be coded using MedDRA® and characterized as pre-treatment and treatment-emergent according to the intake of each treatment. Adverse events with a start date prior to the first dose of IMP in the Run-In Period will be defined as pre-treatment AEs. A TEAE is defined as any AE with a start date on or after the first dose of IMP in Run-In, and on or before the earliest of the following: the last date of infusion (including Run-Out, if applicable) +56 days, final contact date or death. A TEAE is also defined as any unresolved event already present before administration of treatment that worsens in intensity following exposure to the treatment.

Adverse events will be summarized by treatment period and treatment group based on the SS-t. If a participant receives an incorrect treatment per the randomization schedule, the participant will be excluded from the summaries, and the AEs for this participant will be listed only. In such cases these will be noted in the footnotes for the relevant tables. Pre-treatment AEs will not be included in any summaries.

Adverse events will be assigned to the respective treatment period and treatment group based on the start date of the AE. The assignment of AEs to a given treatment period is summarized in Appendix 4 Section 8.4. The treatment groups will be summarized per treatment period in the following way:

- Run-In:
  - PBO (All 3 sequences)
- Treatment Period 1
  - RLZ (Sequence 1)
  - Pooled PBO (Sequence 2 and 3)
- Treatment Period 2

---

- RLZ/RLZ (Sequence 1)
- PBO/RLZ (Sequence 2)
- PBO/PBO (Sequence 3)
- Run-Out and SFU (pooled)
  - RLZ/RLZ (Sequence 1)
  - PBO/RLZ (Sequence 2)
  - PBO/PBO (Sequence 3)

The total N within the summary tables will correspond to the number of participants randomized to the respective treatment sequence who receive at least one dose of IMP in the given treatment period or who entered the SFU period.

For details regarding partial dates, see Appendix 2 [Section 8.2](#).

The number and percentage of participants who experience TEAEs will be summarized by MedDRA™ SOC, HLT, and PT as described above.

Summaries of TEAEs will include the following:

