- Incidence of overall TEAEs (overview including number and percentage of study participant with any TEAEs, serious TEAEs, discontinuations due to TEAEs, permanent withdrawal of study medication due to TEAEs, drug related TEAEs, severe TEAEs and TEAEs leading to death; event counts will also be included)
- Incidence of any TEAEs
- Incidence of any serious TEAEs
- TEAEs leading to permanent withdrawal of IMP
- Incidence of severe TEAEs
- Incidence of treatment-related TEAEs
- Incidence of TEAEs by maximum causal relationship with IMP
- Incidence of TEAEs by maximum intensity
- Incidence of serious TEAEs by maximum causal relationship with IMP
- Incidence of serious TEAEs by causal relationship
- Incidence of fatal TEAEs by causal relationship with IMP
- Incidence of non-serious TEAEs above reporting threshold of 5% of study participants
  - For the purpose of this table, the 5% reporting threshold will be considered based on all TEAEs reported within each of the following groups:
    - PBO Run-In
    - PBO Treatment Period 1
    - RLZ Treatment Period 1

---

- PBO/PBO Treatment Period 2, Run-Out, SFU
- PBO/RLZ Treatment Period 2, Run-Out, SFU
- RLZ/RLZ Treatment Period 2, Run-Out, SFU

ie, non-serious TEAEs occurring with incidence >5% within any of the above groups will be included.

- Incidence of drug-related TEAEs (overview including number and percentage of study participant with any drug-related TEAEs, serious drug-related TEAEs, discontinuations due to drug-related TEAEs, permanent withdrawal of study medication due to drug-related TEAEs, severe drug-related TEAEs and drug-related TEAEs leading to death; event counts will also be included)
- Incidence of drug-related TEAEs by preferred term
- Incidence of serious drug-related TEAEs by preferred term

In summaries including relationship, the following relationships will be summarized: 'Not related', 'Related'. Participants who experience the same event multiple times will be included in the most related category for tabulations by maximum relationship. Events with missing relationship will be considered as 'Related' but recorded as missing in the listings.

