- The first occurrence of treatment-emergent ADA positivity: cumulative number and percentage of TE-ADA positive participants (category 7) who are ADA positive for the first time based on samples collected over the entire study duration, including SFU.
- Summary table of mean maximum percentage change from Baseline in total IgG summarized by ADA participant categories (1-6) for the following:
  - Sequence 1, Treatment Period 1 (RLZ 12 weeks) using ADA participant category based on RLZ 12 weeks exposure and maximum percent change from Baseline in total IgG in Treatment Period 1.
  - Sequence 2, Treatment Period 2 (RLZ 12 weeks) using ADA participant category based on RLZ 12 weeks exposure and maximum percent change from Baseline in total IgG in Treatment Period 2.
  - Sequence 1, Treatment Period 1 and Treatment Period 2 (RLZ 24 weeks) using ADA participant category based on RLZ 24 weeks exposure and maximum percent change from Baseline in total IgG in Treatment Period 2

- Sequence 1 Treatment Period 1 and Sequence 2, Treatment Period 2 (RLZ 12 weeks) using ADA participant category based on RLZ 12 weeks exposure and maximum percent change from Baseline in total IgG in Treatment Period 1 for Sequence 1, and Treatment Period 2 for Sequence 2.
- Summary table of mean change from Baseline in BPI-SF Interference score in Treatment Periods 1 and 2, summarized by ADA participant categories (1-6) for the following:
  - Sequence 1, Treatment Period 1 (RLZ 12 weeks) using ADA participant category based on RLZ 12 weeks exposure and change from Baseline in BPI-SF interference score at Visit 15.
  - Sequence 2, Treatment Period 2 (RLZ 12 weeks) using ADA participant category based on RLZ 12 weeks exposure and change from Baseline in BPI-SF interference score at Visit 27.
  - Sequence 1, Treatment Period 1 and Treatment Period 2 (RLZ 24 weeks) using ADA participant category based on RLZ 24 weeks exposure and change from Baseline in BPI-SF interference score at Visit 27.
  - Sequence 1 Treatment Period 1 and Sequence 2, Treatment Period 2 (RLZ 12 weeks) using ADA participant category based on RLZ 12 weeks exposure and change from Baseline in BPI-SF interference score at Visit 15 for Sequence 1, and Visit 27 for Sequence 2.
- Overall summary table of TEAEs summarized by ADA participant categories 1, 5, 6, and 7 where the participant category is based on ADA data for the entire study duration. This table will include the following:

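### The TEAE tables in SAP 5.6.2 count participants within each period but never once over the whole study or over all rozanolixizumab exposure, and SAP 5.1.2 does not declare this departure from the protocol

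*SAP*

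**What the plan says.** The secondary safety endpoints in SAP Table 1-1 include "Occurrence of TEAEs during the study" and TEAEs leading to withdrawal of IMP.

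Protocol 9.4.1 asks for safety displays by sequence and period, and by treatment and period. It places SFU events from Sequences 1 and 2 under active treatment. It then adds: "The overall frequency during the study period will be presented for each of the safety variables". Protocol 9.1 says that "the SS-t will be used for tabulating AEs by treatment", with events assigned to active according to onset relative to the first active dose.

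SAP 5.6.2 says: "Adverse events will be summarized by treatment period and treatment group based on the SS-t". It introduces the layout with "The treatment groups will be summarized per treatment period in the following way". The columns are:

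- **Run-In:** placebo, all three sequences.
- **Treatment Period 1:** rozanolixizumab (Sequence 1); pooled placebo (Sequences 2 and 3).
- **Treatment Period 2:** one column per sequence.
- **Run-Out and SFU, pooled:** one column per sequence.

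The AEs of focus (AEOF) tables in SAP 5.6.5 are likewise by treatment period and group. SAP 5.1.2 lists changes to baseline definitions, to the timing of the pain and fatigue scores, and the dropping of the placebo-based imputation. It does not mention the overall TEAE frequency.

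**The concern.** A reader of the study report will want to know how many participants had a TEAE, or a particular TEAE, at any time on rozanolixizumab, and how many had one at any time in the study. Both are counts of people, each counted once. SAP 5.6.2 has no column for either, although the first secondary endpoint is worded over the study and the protocol asks for the overall frequency.

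Two things are at stake. The analysis has moved away from the protocol without a declared change. And the main safety tables, which also feed public disclosure through SAP 6.1, leave incidence over full exposure to be inferred from columns that cannot be added.

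**Working it through.** The plan gives no figure to reproduce here, so the check is on what the columns can and cannot yield.

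**Inputs.** 20 participants per sequence and 25% dropout (SAP 1.2); the column layout (SAP 5.6.2); the ADA-category TEAE tables (SAP 5.7).

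**1. Participants exposed to rozanolixizumab.** Sequence 1 plus Sequence 2: 20 + 20 = 40. If 12.5% of Sequence 2 leave before Period 2: 20 + 20 × 0.875 = 37.5. If 25% leave before Period 2: 20 + 20 × 0.75 = 35.

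**2. Columns that can be added.** The first 12 weeks on rozanolixizumab are Sequence 1 in Period 1 and Sequence 2 in Period 2. These are different people, so numerators and denominators add exactly.

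**3. Columns that cannot be added.** Full exposure in Sequence 1 spans Period 1, Period 2 and Run-Out/SFU. In Sequence 2 it spans Period 2 and Run-Out/SFU. The same person can appear in each block. For a sequence of size n, the number with at least one event is known only to satisfy

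largest cell ≤ count ≤ min(n, sum of cells).

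Illustration with assumed counts, n = 20 in each sequence:

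- Sequence 1 cells 10, 8, 5: from 10 to min(20, 23) = 20.
- Sequence 2 cells 9, 4: from 9 to min(20, 13) = 13.
- Together: 10 + 9 = 19 to 20 + 13 = 33 of 40, that is 47.5% to 82.5%.

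The bounds meet when a sequence has events in at most one block. The ambiguity therefore matters for common events, such as headache, and not for isolated ones.

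**4. What SAP 5.7 supplies.** It plans an "Overall summary table of TEAEs summarized by ADA participant categories 1, 5, 6, and 7" and a TEAE incidence table with the same categories. The window is first rozanolixizumab dose to SFU: from Period 1 for Sequence 1 and from Period 2 for Sequence 2. Category 7 combines categories 3 and 4, and category 6 takes everyone not otherwise classified. Categories 1, 5, 6 and 7 are therefore mutually exclusive and cover everyone, and adding across them gives the exact number with any TEAE in that window.

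These tables do not replace the missing display:

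- They exclude Sequence 3, so they give neither a placebo comparator nor a whole-study count.
- They use the SS-r, whereas SAP 5.6 assigns AE tables to the SS-t.
- They plan no pooled total.
- Among the AEOF categories they cover only hypersensitivity, anaphylactic and injection site reactions. Headache and possible aseptic meningitis stay by period.
- SAP 6.1 does not include them among the registry tables.

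**The case against.** The strongest opposing case has several parts.

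- **The protocol sentence can be read differently.** It goes on to frequencies by SOC, HLT and PT, so overall may mean any event as against each term, which the SAP 5.6.2 overview supplies. This reading is possible. But the sentence ties the frequency to the study period, after the by-period displays have already been requested. At the least the SAP should say which reading it adopts.
- **The SAP defaults to the protocol.** SAP 1 says: "Unless specified in the sections below, the study will be analyzed as described in the most recent version of the protocol". SAP 5.6.2 does specify a layout, so it is unclear that the default restores the protocol's count. Details are left to TFL shells that are not part of these documents, and a total column may appear there.
- **Separate periods have a purpose.** They keep placebo concurrent with active, and a whole-study column mixes placebo and active time within Sequence 2. This stands, and is why the period columns should remain.
- **The protocol does not explicitly ask for a pooled rozanolixizumab column.** True; protocol 9.1's assignment by onset relative to first active dose points to one but does not prescribe its layout.

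Three stronger readings are tempting, and the documents do not support them. A reader might infer that the secondary safety endpoint is not produced; in fact the SAP 5.6.2 list includes incidence of any TEAEs and "TEAEs leading to permanent withdrawal of IMP", by period from Run-In to SFU. A reader might infer that incidence on rozanolixizumab cannot be recovered; SAP 5.7 gives it by addition, and the listings carry onset date, period of onset and most recent treatment for every TEAE. A reader might also infer that columns of 20 halve the information on uncommon events. They do not: the two first-12-week columns hold different people and add to 40, and an event in any of them appears in one column or the other.

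**Conclusion.** The point holds as a modest gap in display and declaration. As written, SAP 5.6.2 and 5.6.5 give no TEAE count that includes each participant once over the study or over all rozanolixizumab exposure, the SAP 6.1 registry TEAE tables inherit the same layout, and SAP 5.1.2 is silent. Within a sequence the period columns give only bounds, which can be wide for common events (19 to 33 of 40 in the illustration). That range rests on assumed cell counts and full planned numbers; it shows the mechanism and does not predict a result. No loss of rare-event detection follows. The conclusion also assumes that the unseen TFL shells add no total column; if they do, only the SAP text needs to be brought into line.

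**What to change.** Add two columns to the SAP 5.6.2 overview and SOC/HLT/PT tables and to the AEOF tables in SAP 5.6.5, on the SS-t and counting each participant once:

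1. Any rozanolixizumab: first active dose to SFU, Sequences 1 and 2.
2. Whole study.

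Show participant-weeks at risk for the any-rozanolixizumab column and for placebo. Follow-up is unequal by design: from first active dose to the end of the 5-week SFU it is 24 + 2 + 5 = 31 weeks in Sequence 1 and 12 + 2 + 5 = 19 weeks in Sequence 2. Keep the period columns for the concurrent comparison with placebo, and carry the new columns into the SAP 6.1 registry tables. If the sponsor prefers not to add them, SAP 5.1.2 should declare and justify the omission.

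The cost is a few extra columns and some SAP wording, with no new data. The downside is that the pooled columns have unequal follow-up and must be read with the participant-weeks.

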### **5.6.3 COVID-19 AEs**

Confirmed COVID-19 cases will be recorded as AEs and will be reported under the AE section. An overall summary of TEAEs related to COVID-19 will be provided. This summary table will include the number and percentage of participants, as well as event counts, with any TEAE, any TEAE related to study drug, any severe TEAE, any severe TEAE related to study drug, any TESAE, any TESAE related to study drug, any TEAE leading to treatment discontinuation, any study drug related TEAE leading to treatment discontinuation, any TEAE leading to study withdrawal, and any deaths. In addition, to the above summary, TEAEs related to COVID-19 will be summarized by SOC, HLT, and PT in a separate table. Both COVID-19 AE tables will be summarized by treatment period and treatment group based on SS-t.

MedDRA has a COVID-19 Standardised MedDRA Query (SMQ). The query used in this study will be the broad MedDRA COVID-19 SMQ as defined at the specified analysis time points (see <https://www.meddra.org/COVID-19-terms-and-MedDRA>).

### **5.6.4 AEs of Special Interest and AEs of Special Monitoring**

An AE of special interest (AESI) listing will be produced of Potential Hy's Law, defined as  $\geq 3 \times \text{ULN}$  alanine aminotransferase (ALT) or aspartate aminotransferase (AST) with coexisting  $\geq 2 \times \text{ULN}$  total bilirubin in the absence of  $\geq 2 \times \text{ULN}$  alkaline phosphatase (ALP), by treatment sequence and participant including most recent treatment received prior to the AE.

An AE of special monitoring (AESM) is a product-specific AE, adverse reaction, or safety topic requiring special monitoring by UCB. AESM will be listed.

Following events will be listed under AESM

- Severe and/or serious headache
- Suspected aseptic meningitis

Summaries of the incidence of AESM and incidence of AESI will be generated. AESM and AESI summaries will be based on investigator assessment as recorded on the eCRF and confirmed during data review.

